6.6.5.2. Other laboratory parameters

All other parameters collected on the eCRF will be listed in dedicated listings presenting all corresponding collected information on the eCRF.

- Coagulation: activated partial thromboplastin time (aPTT), prothrombin time (PT) and International Normalized Ratio (INR).
- HCV, HBV, HIV serology
- Urinalysis: Protein, glucose and blood
- Other parameters: Absolute Monocytes, Absolute Eosinophils, Absolute Basophils, Chloride, Total Urea, Uric Acid, Total Protein, C-Reactive Protein, Lactate Dehydrogenase (LDH)
- Cardiac biomarkers: Troponin (cTnT or cTnI)
- Pregnancy test

The listings of laboratory results will be provided for all laboratory parameters. The listings will be sorted by parameters and assessment dates or visits for each patient. Laboratory values that are outside the normal range will also be flagged in the data listings, along with corresponding normal ranges. A listing of CTCAE grading will also be generated for those laboratory tests.

In addition, listings of abnormal values will be provided for hematology, chemistry, urinalysis, coagulation parameters. If there is at least one abnormal assessment for any parameter, all the data for that laboratory parameter will be included into the listing.

For all tests not mentioned above but present in the clinical data, a listing of patients with at least one result for the relevant test will be provided.

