| | | 
Activities for Study Treatment Period footnote 1 and Follow-up Period footnote 1).
 
8. Per United States FDA request, to assess the utility of serum troponin measurements in early detection of myocarditis, a rare and potentially fatal risk associated with avelumab and other check-point inhibitors, the following additions were made to both study arms:
 
 • Mandatory measurement of cardiac troponin levels at screening and at each clinic visit ending on Cycle 4 Day 1 (ie, for a total of 12 weeks), and as clinically indicated (Schedule of Assessments for Study Treatment footnote 12, and Table 6). • Management guidelines for myocarditis (Table 5). • Further information and rationale for this addition in Section 1.2.2.1. 
9. To adequately monitor for disease progression, clarified that chest, abdomen, and pelvic CT or MRI scans are required at each tumor assessment time point and for all patients (Schedule of Activities for Study Treatment Period footnote 16 and Follow-up Period footnote 13; and Sections 3.1.2 and 7.7).
 
10. Revised the requirement for a screening bone scan (or ¹⁸F¹⁸FDG-PET scan) to allow alternate modalities (eg, MRI) per local standard of care, as ¹⁸F¹⁸FDG-PET scan is not a permissible alternate for bone imaging at some centers and MRI in some countries is the preferred method for bone imaging instead of bone scans (Schedule of Activities for Study Treatment Period footnote 16 and
 |

| Document | Version Date | Summary of Changes |
|----------|--------------|--|

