| Laboratory Studies | | | | | |
| Coagulation ⁸ | X | X | X | X | |
| Hematology ⁸ | X | X | X | X | |
| Blood Chemistry (full and core) ^{8,9} | X | X ^{8,9} | X ^{8,9} | X ^{8,9} | |
| Thyroid Function and ACTH Tests ¹⁰ | X | X (at Cycles 3, 5, 7, etc.) | | X (at Cycles 3, 5, 7, etc.) | |
| Serum/Urine Pregnancy Test ¹¹ | X | X | X | | |
| Troponin ¹² | X | X (Cycles 1-4 and as clinically indicated) | X (Cycles 1-3 and as clinically indicated) | X (Cycles 1-4 and as clinically indicated) | |
| HBV, HCV Tests | X | If clinically indicated | | If clinically indicated | |
| HIV test ¹³ | X | | | | |
| Urinalysis ¹⁴ | X | If clinically indicated | | If clinically indicated | |
| 12-Lead ECG ¹⁵ | X | If clinically indicated | | If clinically indicated | |
| Disease Assessments | | | | | |
| Tumor Assessments (including scans) ¹⁶ | X | X (Q8W for the 1 st yr after randomization and Q12W thereafter) | | X (Q8W for the 1 st yr after randomization and Q12W thereafter) | |
| Other Clinical Assessments | | | | | |
| Adverse Events ¹⁷ | | X | X | X | X ¹⁸ |
| Concomitant Medications/Treatments ¹⁹ | X | X | X | X | X ¹⁸ |

| Visit Identifiers ¹ | Screening | Study Treatment (1 cycle = 4 weeks) | | | |
|--|-----------|---|---|--------------------------------|---|
| | | Arm A | | Arm B | |
| | | Within 28 Days Prior to Randomization | Cycle 1 Day 1 Cycle ≥2 Day 1 (±3 days) | Day 15 (±3 days) All Cycles | Cycle 1 Day 1 Cycle ≥2 Day 1 (±3 days) |
| Patient Reported Outcomes (NCCN-FACT FBISI-18, EQ-5D-5L) ²⁰ | | X | | X | |
| Randomization & Study Treatment | | | | | |
| Randomization ²¹ | X | | | | |
| Avelumab (Arm A only) ²² | | X | X | | |
| Best Supportive Care (BSC) ²³ | | X (Throughout study treatment) | | X (Throughout study treatment) | |
| Other Samplings | | | | | |
| Archival FFPE Tumor Tissue ²⁴ | X | | | | |
| Mandatory Recent FFPE Tumor Tissue Block or de novo biopsy ²⁵ | X | | | | |
| Banked Blood Biospecimen for Genotyping ²⁶ | | X (Cycle 1 only) | | X (Cycle 1 only) | |
| Banked Blood Biospecimens for Exploratory Assessments ²⁷ | | X (Cycle 1, 2, 3 & 5) | X (Cycle 1 only) | X (Cycle 1, 2, 3 & 5) | |
| Pharmacokinetics ²⁸ | | X (Cycles 1-3, 5, 7, 9, 11 & 13) | X (Cycles 1-3) | | |
| Anti-Avelumab Antibodies and Neutralizing Antibodies ²⁹ | | X (Cycles 1-3, 5, 7, 9, 11 & 13) | X (Cycles 1-3) | | |

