| 11. | Serum/Urine Pregnancy Test: For female patients of childbearing potential, a serum pregnancy test, with sensitivity of at least 25 mIU/mL, will be performed on two occasions prior to starting study treatment: once at the start of screening and once at the Cycle 1 Day 1 visit for Arm A patients immediately before study treatment administration. Additional pregnancy tests (serum or urine) will also be routinely repeated for Arm A patients prior to each avelumab dose during the active treatment period, at the End of Treatment/Withdrawal visit, and additionally whenever one menstrual cycle is missed or when potential pregnancy is otherwise suspected. Additional pregnancy tests may also be undertaken if requested by Institutional Review Board (IRB)/Ethics Committees (ECs) or if required by local regulations. Results of the pregnancy test should be available prior to each dosing. After randomization, pregnancy tests will be performed only for Arm A patients. See Section 7.1.1 . |
| 12. | Cardiac Troponin (cTn): Measurement of cTnT is preferred; however, cTnI may be substituted where cTnT is not available at the local laboratory. The same subunit (cTnT or cTnI) measured during screening should be measured consistently throughout the study for any given patient. During screening, clinically significant positive results should be further assessed as per local standard of care to rule out concurrent cardiac conditions which could make the patient ineligible for the study per the exclusion criteria. During the study, clinically significant new elevations suggestive of myocarditis should be assessed as per Table 5 . Additional tests should also be performed when clinically indicated. See Table 6 . |
| 13. | HIV test: HIV serology test is required at screening unless not permitted by local laws and regulations. If indicated, supplemental testing may be performed per standard practice to confirm an HIV infection. |
| 14. | Urinalysis: Required only at Screening and End of Treatment. To be performed as clinically indicated at other time points. Required tests are listed in Table 6 . |

- 15. 12-Lead Electrocardiogram (ECG):** All patients require a single ECG measurement at screening. Additional ECGs may be performed as clinically indicated. Clinically significant new findings seen on follow-up ECGs should be recorded as adverse events.

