Cases of severe or fatal myocarditis also have been reported with other immune checkpoint inhibitors, including pembrolizumab, nivolumab, and ipilimumab,²⁰⁻²⁴ either as single adverse events or in the context of more complex autoimmune syndromes. For both ipilimumab and nivolumab, myocarditis is reported in the prescribing information with a frequency of <1%.^{25,26}

Given these reports, routine troponin measurements are being implemented in selected avelumab studies, including Protocol B9991001. Cardiac troponin (cTn) is a sensitive marker of myocardial injury and may aid in the identification of patients potentially experiencing myocarditis; however, the utility of routine troponin monitoring for the early detection of myocarditis is currently unknown. In addition to cTn monitoring, guidelines for the management of suspected or confirmed myocarditis and relevant avelumab management instructions are provided in [Table 5](#).

Avelumab Pharmacokinetics: Avelumab pharmacokinetics and dose proportionality following the first 1-hour infusion have been characterized in 77 mainly Caucasian patients treated in the dose escalation and expansion cohorts of Study EMR 100070-001 by standard non-compartmental analysis. This analysis revealed that the exposure parameters of C_{max} and AUC_{τ} increased with dose in a linear fashion across the 1, 3, 10 and 20 mg/kg doses. The apparent half-life tends to increase with the dose, presumably linked to target-mediated disposition. Taking into account the variability, the half-lives of the 10 and 20 mg/kg doses were similar (mean half-lives of 102 and 120 hours, respectively), indicating that target mediated elimination does not increase at these doses. This implies that target occupancy is likely to be high at these two doses throughout the dosing interval.

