8.5. Abnormal Test Findings

The criteria for determining whether an abnormal test finding should be reported as an AE are as follows:

- Test result is associated with accompanying symptoms; and/or
- Test result requires additional diagnostic testing or medical/surgical intervention; and/or
- Test result leads to a change in study dosing outside of protocol-stipulated dose adjustments or discontinuation from the study, significant additional concomitant drug treatment, or other therapy; and/or
- Test result is considered to be an AE by the investigator or sponsor.

Merely repeating an abnormal test, in the absence of any of the above conditions, does not constitute an AE. Any abnormal test result that is determined to be an error does not require reporting as an AE.

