Albumin (hypoalbuminemia), Alkaline Phosphatase (alkaline phosphatase increased), Alanine Aminotransferase (ALT) (ALT increased), Amylase (serum amylase increased), Aspartate Aminotransferase (AST) (AST increased), Total Bilirubin (blood bilirubin increased, Cholesterol (cholesterol high), Creatinine (creatinine increased), Creatine Kinase (CPK increased), Potassium (hypokalemia/ hyperkalemia), Sodium (hyponatremia/ hypernatremia), Magnesium (hypomagnesemia/hpermagnesemia), Calcium (hypocalcemia/ hypercalcemia), Glucose (hypoglycemia/hyperglycemia), Gamma Glutamyl Transferase (GGT) (GGT increased), Lipase (lipase increased), Phosphates (hypophosphatemia), Triglycerides (hypertriglyceridemia).

Parameters with NCI-CTC grades not available:

Hematology and chemistry evaluations which cannot be graded per CTCAE criteria will be summarized as frequency (number and percentage) of patients with:

- shifts from baseline normal to at least one result above normal during on-treatment period

- shifts from baseline normal to at least one result below normal during on-treatment period

In this study, these apply to the following parameters:

- Thyroid function and ACTH tests: Free T4, Thyroid Stimulating Hormone (TSH), ACTH

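### Troponin is planned for listings only, so no laboratory table gives the by-arm rate of new elevations

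*SAP*

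**What the plan says.** **SAP 6.6.5.2 (other laboratory parameters).** The group containing "Cardiac biomarkers: Troponin (cTnT or cTnI") is handled as follows: "All other parameters collected on the eCRF will be listed in dedicated listings presenting all corresponding collected information on the eCRF". Listings flag out-of-range values and show the normal ranges. A further listing of abnormal values covers hematology, chemistry, urinalysis and coagulation; cardiac biomarkers are not named.

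**SAP 6.6.5.1 (hematology and chemistry).** The tables of CTCAE grade, baseline-to-worst-grade shift and new or worsening abnormality apply to a closed list of tests without troponin. The summary of shifts from normal, for tests that cannot be graded, is limited to "Thyroid function and ACTH tests: Free T4, Thyroid Stimulating Hormone (TSH), ACTH".

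**Protocol.** Section 1.2.2.1 introduces routine troponin after reports of myocarditis and says that "the utility of routine troponin monitoring for the early detection of myocarditis is currently unknown". The Schedule of Activities has Day 1 draws in both arms, "X (Cycles 1-4 and as clinically indicated"), and Day 15 draws in Cycles 1 to 3 in Arm A only. Footnote 12 says that "clinically significant new elevations suggestive of myocarditis should be assessed as per" Table 5. Section 9.5 foresees shift tables of laboratory abnormalities without naming tests.

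**The concern.** Troponin is not an ordinary safety test here. It was added for a specific suspected toxicity, its usefulness is described as an open question, and it is drawn in a randomised control arm that receives no avelumab. That arm is the natural source of a background rate for troponin rises in this population. Without it, an elevation rate under avelumab is hard to interpret.

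The adverse event tables are not a full substitute. Under Protocol 8.5 an abnormal result becomes an event if it meets certain conditions, such as needing further diagnostic testing, and "Merely repeating an abnormal test, in the absence of any of the above conditions, does not constitute an AE". Whether a rise is worked up is decided by investigators who know the treatment arm. The programmed definition of immune-related events (SAP Appendix 1) also requires corticosteroid or other immunosuppressant treatment, or hormone replacement for endocrinopathies, so an isolated rise would not normally qualify.

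At stake is the interpretability of one safety measurement. Overall survival is not involved.

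**Working it through.** The plan gives no numerical figure for troponin, so there is none to reproduce. The check has three parts.

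**1. Tracing troponin through the planned outputs**

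| Output | Scope in the SAP | Troponin? |
|---|---|---|
| Grade, shift and new/worsening tables (6.6.5.1) | Closed list of gradable tests | No |
| Shift-from-normal summary (6.6.5.1) | Free T4, TSH, ACTH | No |
| Listings of abnormal values (6.6.5.2) | Four named groups | No |
| Dedicated listings (6.6.5.2) | Includes cardiac biomarkers | Yes, as a listing |
| Treatment-emergent event tables (6.6.1.1) | Rises reported as events | Partly |

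One general sentence near the start of 6.6.5.1 says that results outside CTCAE are presented as below, within or above normal limits. Protocol Table 6 prints troponin in its chemistry column, so the sentence might be thought to cover it. I read it as not doing so: 6.6.5.2 places troponin explicitly among the other parameters, and the shift summary names the tests to which it applies.

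**2. Why a crude count from the listings would mislead**

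Taking Cycle 1 Day 1 as baseline, the scheduled draws are:
- Arm A: C1D15, C2D1, C2D15, C3D1, C3D15, C4D1 = 6
- Arm B: C2D1, C3D1, C4D1 = 3

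Assume the same chance q of an elevation at every draw in both arms, with independent draws. The documents give no value for q. With k draws completed, P(any elevation) = 1 − (1 − q)^k. For example, at q = 1%: 1 − 0.99^6 = 5.9% and 1 − 0.99^3 = 3.0%.

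For attrition, assume that sampling stops at progression and that progression-free survival is exponential with a median of 5.3 months in both arms (the placebo median of the lapatinib maintenance trial cited in the Protocol Summary and Section 1.2.3.1). The share remaining at week w is 0.5^(t/5.3), with t = 7w/30.4375 months. At weeks 2, 4, 6, 8, 10 and 12 this gives 0.94, 0.89, 0.84, 0.79, 0.74 and 0.70. Averaging 1 − (1 − q)^k over the resulting number of draws gives the last column.

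| q (assumed) | No attrition, A v B | With attrition, A v B |
|---|---|---|
| 0.5% | 3.0% v 1.5% | 2.4% v 1.2% |
| 1% | 5.9% v 3.0% | 4.8% v 2.3% |
| 2% | 11.4% v 5.9% | 9.3% v 4.7% |

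The ratio is about two throughout, with no drug effect.

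**3. What a matched table could show**

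With 668 patients randomised 1:1 there are 334 per arm. The evaluable number is unknown: troponin became mandatory with Amendment 3 (19 December 2016), the original protocol is dated 29 October 2015, and patients leave before C4D1. I assume 50%, 70% or 100% evaluable. The 95% half-width for a risk difference with rate p in both arms is 1.96 × √(2p(1 − p)/n), a normal approximation that is rough at p = 1%.

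| Evaluable | n per arm | Half-width at p = 3% | If half use each subunit: n, half-width |
|---|---|---|---|
| 100% | 334 | 2.6 points | 167, 3.7 points |
| 70% | 234 | 3.1 points | 117, 4.4 points |
| 50% | 167 | 3.7 points | 84, 5.2 points |

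Over p = 1% to 5% the range is 1.5 to 4.7 points overall and 2.1 to 6.6 per subunit. For the Arm B background rate alone, 10/334 has an exact 95% interval of 1.4% to 5.4%, and 5/167 one of 1.0% to 6.8%.

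**The case against.** The strongest reply is that listings are a defensible choice. The usefulness of troponin is neither an objective nor an endpoint. The statement that it was added "to assess the utility of serum troponin measurements in early detection of myocarditis" stands in the amendment history, while Section 1.2.2.1 also describes it as an aid to identifying individual patients. Early detection is a question of case-level timing, which listings serve. Myocarditis at the frequency below 1% that the protocol cites for ipilimumab and nivolumab would mean about 3 or fewer of 334 patients. Rises that matter clinically should become adverse events, because Table 5 calls for a cardiology consult and hospitalisation, and footnote 12 does not distinguish the arms. The proposed table mixes local assays and has limited precision.

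Most of this stands and is why the point is minor. It does not remove the gap: rises not judged to need work-up have no by-arm laboratory summary, and those are what a background rate is made of.

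Three stronger readings are tempting, and the documents support none of them:
- **That the rate is unavailable or has to be tallied manually.** The values are on the eCRF and flagged in listings, so the rate can be programmed; it is simply not a specified analysis.
- **That the SAP contradicts the protocol.** Protocol 9.5 is broader but does not name troponin, and SAP Section 2 allows the SAP to modify the protocol's plans.
- **That the event tables are biased by a known amount.** Open-label work-up makes a difference between arms possible, but nothing in the documents shows that it occurs or how large it would be.

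**Conclusion.** The point holds as a reporting gap. No planned laboratory table gives the by-arm rate of new troponin elevations; the event tables give only the part that meets the criteria in Protocol 8.5. A later count that ignores the 6 v 3 draw schedule would show about twice the rate in Arm A with no true difference. That size rests on assumed per-draw rates, independent draws and, in one version, assumed attrition.

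The gain is modest: a described background rate with a half-width of about 2.6 to 3.7 points at an assumed 3%, wider per subunit. Survival conclusions do not change. The Safety Review Plan and the separate SAP for the data monitoring committee were not available and might contain such a summary. I would ask the sponsor to consider the change, not require it.

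**What to change.** Add troponin to the shift-from-normal summary in SAP 6.6.5.1:
- By arm, and separately for cTnT and cTnI, give the number and percentage of patients with a normal baseline and at least one on-treatment value above the local upper limit of normal. Show the evaluable number (baseline plus at least one on-treatment result).
- Base the between-arm comparison on the visits common to both arms: C2D1, C3D1 and C4D1. Count Arm B values only before any crossover dose of avelumab.
- Beside it, show all on-treatment values, including Arm A's Day 15 draws and clinically indicated draws, as a descriptive summary that states the unequal sampling.
- Describe any overlap with myocarditis events case by case.
- Label the tables post hoc if they are added after the interim readout.

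The cost is a short SAP edit and two tables from data already collected. Incidental elevations will appear in both arms, and results come from local assays with two subunits. The matched table also omits Arm A's Day 15 samples: 3 × 334 = 1,002 of 6 × 334 = 2,004 scheduled draws at most, or about 841 of 1,632 under the attrition assumption. That is why the all-values summary stays beside it.

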6.6.6. Vital signs

Weight for the purposes of dose calculation will be recorded at screening and within 3 days pre-dose Day 1 and Day 15 of each cycle. Height will be measured at screening only.

Vital sign summaries will include all vital sign assessments from the on-treatment period. All vital sign assessments will be listed, and those collected outside the on-treatment period will be flagged in the listing.

All vital sign parameters will be summarized using descriptive statistics (mean, SD, median, Q1, Q3, minimum, and maximum) of actual values and changes from baseline for each visit over time. End of Treatment visit will be summarized separately. The changes computed will be the differences from baseline.

6.6.7. Electrocardiogram

ECGs in the B9991001 study are collected only when clinically indicated. Patients with qualitative ECG abnormalities will be listed.

6.6.8. ECOG Performance Status

The ECOG shift from baseline to highest score during the on-treatment period will be summarized by treatment arm.

7. INTERIM ANALYSES

7.1. Introduction

The goals of the interim analyses are to allow early stopping of treatment arm(s) for futility or efficacy and to potentially adjust the sample size. The interim analysis of OS will be performed as described in Sections 5.1.1 and 5.1.2 using the methodology described in Section 6.1.1.1 for OS.

Unblinded results from the interim analysis for OS will not be communicated to the Sponsor's clinical team or to any party involved in the study conduct (apart from the independent statistician and E-DMC members) until the E-DMC has determined that either (i) OS analysis has crossed the pre-specified boundary for efficacy or (ii) the study needs to be terminated due to any cause, including futility or safety reasons. Further details will be described in the E-DMC charter.

7.2. Interim Analyses and Summaries

At each analysis time point, the critical boundaries for the group sequential test will be derived from the predefined spending function(s) as described in Section 5.1. The calculations of boundaries will be performed using EAST.

7.2.1. Interim analysis for OS

Let $u(t_1)$ and $u(t_F)$ denote the upper critical boundaries based on the test statistics Z_1 and Z_F for efficacy at the interim and the final analysis, respectively, and let $l(t_1)$ and $l(t_F)$ denote the lower critical boundary for futility at the interim and final analysis, respectively. For the final analysis, $l(t_F)=u(t_F)$.

The critical values $u(t_1)$ and $l(t_1)$ for the interim analysis of OS are determined such as

$$P_0(Z_1 \geq u(t_1)) = \alpha(t_1) \quad \text{and} \quad P_a(Z_1 \leq l(t_1)) = \beta(t_1) ,$$

where P_0 and P_a denote the probabilities under the null hypothesis and the alternative hypothesis, respectively, and $\alpha(t_1)$ and $\beta(t_1)$ denote the α and β spent, respectively, based on

the predefined spending functions at information fraction t_1 (t_1 is calculated as the ratio of the number of OS events observed at the time of the cut-off for the interim analysis and the total number of OS events targeted for the final analysis).

The boundary for the final efficacy analysis will be calculated such that

$$\alpha(t_1) + P_0(Z_1 < u(t_1), Z_F \geq u_F) = \tau$$

$\tau=0.015$ for 'all patients' population,

$\tau=0.01$ for 'patients with PD-L1-positive tumors' population

As described in [Section 5.1.2](#), if the number of OS events in the final analysis deviates from the target number of OS events, the final analysis criteria will be determined as above taking into account the actual alpha spent at the interim analysis and the actual correlation between the two test statistics Z_1 and Z_F , so that the overall one-sided significance level across all analyses and comparisons is preserved at 0.025.

